1.4 OBJECTIVES

The primary objective of this study is to evaluate the difference in postoperative bleeding between two study groups, FDA cleared MONTAGE and standard of care (no bone hemostat), and the extent to which any transfusion is needed and blood loss is measured through drop in hematocrit (HCT), as well as wound drain output, if utilized. As an exploratory evaluation of the primary endpoints a calculation will be made of blood loss for the first 7 days following surgical procedure as assessed by a multivariate combination of these measures of blood loss.

The secondary objective is the stability of the construct, as measured by whether the correction has maintained stability at 1-year and 2-years post surgery. Each incidence of instability will be categorized as belonging to one of the following groups: 1) hardware malplacement, 2) loosening or dislodgment, 3) nonunion or nonfusion with hardware fracture 4) nonunion or nonfusion without hardware fracture and 5) perihardware fracture.

Each osteotomy site will be assessed using X-rays and with computed tomography (CT) scans – performed at 12 months post surgery. Failure of fusion will be determined to be present if an area of bone apposition lucency greater than 2mm in thickness is present.

Secondary objectives will also include:

- The formation of new bone, as measured by CT scans at 1-year post surgery,
- Evaluation of Visual Analog Scale (VAS) back and leg pain, Oswestry Disability Index (ODIv2.1a), and SRS-22 scores, which will be recorded during the study and compared between the two groups.
- Evaluation of work status.
- Antifibrinolytics use and type will be recorded during the study and compared between the two groups

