4.2.3.6 Visit #7: Follow-up visit (Week 52)

Radiographs- standing ap and lateral scoli xrays will be completed and centrally read by independent evaluators.
VAS back and leg, ODIv2.1a and SRS-22 scores will be collected
Current pain medications/dosing will be collected.
Angular correction and gap will be measured.
A CT scan will be taken to evaluate screw loosening and other measures of bone healing.
Adverse Events will be recorded.

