6. STATISTICAL DESIGN

6.1 DESIGN

This is a parallel group, randomized, open, multicenter, prospective study in subjects with spinal deformities requiring a PSO procedure at a single level. Patients will be randomized 1:1 to receive either MONTAGE or no bone hemostat. Within each randomization study group, patients will be stratified according to their smoking status (non-smokers versus current smokers).

The primary objective of this study is the evaluation of post-operative blood loss in the week following surgery.

The secondary outcome will be the stability of the construct, as measured by the gap between the repaired osteotomy edges. In addition, observations will be made regarding whether the hardware repair has been maintained, and if the screws have loosened, and if the inserted rods are intact. Each repair complication will be categorized as belonging to one of the following groups: 1) hardware malplacement, 2) loosening or dislodgment, 3) nonunion or nonfusion with hardware fracture 4) nonunion or nonfusion without hardware fracture 5) peri-hardware fracture. These complications will be measured with imaging, including CT scans performed at 1-year. Fusion failure will be determined to be present if an area of perihardware lucency greater than 2 mm in thickness is present.

Malplacement of hardware will be considered present when an abnormal hardware position with hardware impingement on an important structure such as nerve or vessel is present.

Other secondary objectives will include:

- The formation of new bone at the osteotomy site, measured in mms at 1-year post surgery at the osteotomy site.
- VAS back and leg, Oswestry Disability Index (ODIv2.1a), and SRS-22 scores which will be recorded during the study and reported as outcomes scores, and compared between the two groups.
- Analysis of the MONTAGE/vertebral body interface, evaluating whether bony substitution has occurred at 1-year post-surgery. The presence or absence of bony resorption around the MONTAGE will also be reviewed.
- The use and type of antifibrinolytics will be compared between the two groups.

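### The five-group coding of construct complications is not exhaustive (hardware fracture with union, and loss of correction alone, have no group), and the section 6.1 lucency criterion makes loosening and nonunion overlap

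*Combined protocol and SAP*

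**What the plan says.** Section 1.4 makes stability of the construct the secondary objective, "as measured by whether the correction has maintained stability at 1-year and 2-years post surgery". It then sets the coding rule: "Each incidence of instability will be categorized as belonging to one of the following groups". The groups are "1) hardware malplacement, 2) loosening or dislodgment", then "3) nonunion or nonfusion with hardware fracture 4) nonunion or nonfusion without hardware fracture", then "5) perihardware fracture".

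Section 6.1 repeats the five groups, now for each repair complication: "nonunion or nonfusion with hardware fracture 4) nonunion or nonfusion without hardware fracture 5) peri-hardware fracture" closes its list. It measures stability by the gap between the osteotomy edges and adds that "observations will be made regarding whether the hardware repair has been maintained, and if the screws have loosened, and if the inserted rods are intact". It defines malplacement; the other four groups get no definition of their own.

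Both sections give a criterion for failed fusion, each a lucency thicker than 2 mm. Section 1.4 locates it at the bone apposition, section 6.1 around the hardware.

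On imaging, the Week 52 visit (section 4.2.3.6) says: "A CT scan will be taken to evaluate screw loosening and other measures of bone healing". The Week 104 visit (section 4.2.3.7) and Appendix I schedule radiographs but no CT. Section 6.3.2 labels all secondary analyses exploratory.

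**The concern.** A rule that assigns each event to one group works only if every event has a group and no single finding belongs to two. Neither condition is met.

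- **Gaps.** Section 6.1 asks whether the rods are intact, but the list gives a broken rod a place only if the osteotomy has also failed to unite. Section 1.4 judges stability by maintained correction, but the list has no place for correction lost while union and hardware are sound. With no 'other' option, a reader must leave such an event uncoded or put it in a group that does not describe it.
- **Overlap.** If lucency around hardware defines failed fusion, the same image of a loose screw can support two codes.

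The risk is that the complication table misstates which failures occurred in each arm. Nonunion is the entry most worth protecting: section 1.3 gives possible interference with fusion as the probable reason why bone hemostats have not been standard care, and section 4.1.2 sets out to show that the device does not impair the repair.

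**Working it through.** **1. Plan figures.** The plan states no event rate or count for these complications, so there is none to reproduce. The only planning figure used here is the arm size in section 3.1. With a difference of 500 mL, an SD of 500 mL (reading the +/- as an SD), two-sided alpha 0.05 and 90% power:

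n = 2 × (1.960 + 1.282)² × (500/500)² ≈ 21.0, rounded up to 22 per arm; 22 / 0.90 = 24.4, rounded up to 25.

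This matches the stated 25 per arm, 50 in total.

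**2. Each finding taken singly.** This follows the per-incidence wording. It assumes that perihardware fracture means fracture of bone next to the hardware.

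| Finding alone | Group |
|---|---|
| Malplacement | 1 |
| Loosening or dislodgment | 2 |
| Nonunion, hardware intact | 4 |
| Hardware fracture, osteotomy united | none (group 3 also needs nonunion) |
| Perihardware fracture | 5 |
| Loss of correction, union, hardware intact | none |

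Two of the six have no group.

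**3. All combinations.** Six yes/no findings give 2⁶ − 1 = 63 non-empty patterns. Groups 3 and 4 split nonunion between them, so the number of groups met equals the number present among malplacement, loosening, nonunion and perihardware fracture. Each such combination occurs with 2 × 2 = 4 settings of hardware fracture and loss of correction.

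- No group: none of the four present, and at least one of the other two: 4 − 1 = 3 patterns (hardware fracture alone, loss of correction alone, both).
- Exactly one group: 4 × 4 = 16 patterns.
- Two or more groups: (16 − 1 − 4) × 4 = 44 patterns.

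Check: 3 + 16 + 44 = 63. These counts describe the scheme and are not frequencies. The 44 are whole-subject combinations; where the findings are separate incidences, each can have its own code, so 44 does not measure overlap under the rule as written.

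**4. Overlap within one finding.** Take a loose screw with a surrounding lucent zone thicker than 2 mm. It is loosening, group 2. Under section 6.1 the same zone meets the fusion-failure criterion, so it is also group 3 or 4, depending on whether hardware is broken. Under section 1.4 it is not fusion failure unless there is also lucency at the bone apposition. One image therefore yields different codes according to the section followed, and neither section gives a precedence or multiple-coding rule.

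**5. Union status at two years.** Post-operative radiographs are scheduled at Weeks 2, 6, 12, 24, 52 and 104, six visits; post-operative CT is scheduled once, at Week 52. Groups 3 and 4 need a union verdict. For a rod that breaks after Week 52, the plan does not say how union is decided or allow an undetermined value.

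**6. Size per subject.** 1/25 = 4 percentage points in an arm, and 2/25 = 8. After the planned 10% loss, 25 × 0.90 = 22.5; with 22 evaluable, 1/22 = 4.5 points.

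**The case against.** The best reply is that little depends on this table. The stated test for harm is the residual gap on the 1-year CT, compared by t test (Summary and section 4.1.2), and section 6.1 itself measures stability by the gap. The five groups have no named test and fall under analyses labelled exploratory. That stands, and it limits the consequence.

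A reader might infer that failures vanish from the trial. The documents do not support this. Section 6.1 has rods and screws observed in their own right, the visits from Week 6 to Week 104 measure angle and gap, and section 6.3.3 lists all adverse events. Only the classification lacks a place for them.

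A reader might also infer that loose screws and nonunion in one patient can never both be coded. Section 1.4 works per incidence and section 6.1 per complication, so two separate findings can each have a code. The conflict remains only where one finding meets two groups, as in step 4.

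Nor does the nonunion count rest wholly on which code is entered first. Fusion failure has its own lucency criterion outside the groups and can be counted from it. The weakness is that the two sections state that criterion differently.

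That malplacement is a positioning finding is a minor matter: section 6.1 uses the broader term for complications, defines malplacement, and gives it its own group.

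**Conclusion.** The classification is defective as written in both sections. It has no group for hardware fracture with a united osteotomy or for loss of correction alone, no 'other' option, and, through the section 6.1 lucency wording, a real overlap between loosening and nonunion.

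The effect stops at the descriptive, exploratory table of construct complications. The gap comparison, the primary blood-loss endpoint and the sample size are unaffected. It would go too far to call this table the trial's main evidence on harm to the construct.

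Each miscoded subject is worth about 4 to 4.5 percentage points in an arm. How many there would be cannot be computed, because the documents give no rates of union, hardware fracture, loosening or loss of correction. The conclusion assumes that perihardware fracture refers to bone. If a reader took it, or dislodgment, to include a broken rod, the event would get a code, but one that conceals what happened.

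**What to change.** In sections 1.4 and 6.1, replace the single-choice list with separate items recorded per subject at Weeks 52 and 104, several of which may be present:

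- union status, with undetermined as an allowed value;
- hardware fracture;
- loosening or dislodgment;
- perihardware fracture;
- malplacement.

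Report nonunion and hardware fracture as their own rows by arm.

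Report loss of correction as change in the angle already measured. Use a yes/no item only if its threshold is fixed before the images are read; the plan has none now, so such an item could not be scored.

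Reconcile the two lucency criteria so that one definition of fusion failure applies at the osteotomy, and lucency around a screw is not read as both loosening and nonunion. Merely adding an extra group and an 'other' option would close the gaps but leave this overlap.

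The cost is protocol wording, a revised read form and a few more table rows. The images and the two readers stay the same.

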2. INVESTIGATIONAL PRODUCT/TREATMENT

2.1 DESCRIPTION OF INVESTIGATIONAL PRODUCT UNDER TEST

MONTAGE is a settable (hardening) bioabsorbable polymer and hydroxyapatite/beta tricalcium phosphate based putty, used in the control of bleeding from bone during spine, orthopedic, craniomaxillofacial, thoracic and other surgical procedures, and has been FDA cleared.

It is easy to manipulate and in all instances, as reported in preclinical studies, resulted in immediate and complete cessation of defect bleeding. The putty hardens within minutes after application, remaining secure in place, without being dislodged or dissolved.

In rabbit diaphyseal femoral defects (N=12), MONTAGE putty was implanted; and after 4 weeks each defect was evaluated by histopathology. The microscopic evaluation demonstrated no significant signs of inflammation or fibrosis, while there was indication that new bone formation occurred.

MONTAGE has been used in many clinical settings, including during spinal and sternotomy procedures. Long-term follow-up in various settings has not demonstrated any adverse events of significance. (9, 10, 11, 12).

2.2 PACKAGING AND LABELING

MONTAGE will be supplied terminally sterilized in individual packaged units of 5cc (10grams). MONTAGE should be stored at room temperature.

2.3 METHOD OF DISTRIBUTION

Delivery of all study materials (e.g. product, CRFs, etc.) to the study centers will be arranged by the Sponsor's Clinical Research Associates (CRA).

2.4 ACCOUNTABILITY

The investigator or designated individual will maintain inventories that will detail receipt, use, return and collection of Montage trial supplies by the company. The use inventory log will be used to document which products (batch, expiry, and quantity) were used on which subjects for traceability.

3. TRIAL SUBJECT POPULATION

3.1 NUMBER OF SUBJECTS

A multicenter study will be undertaken in the US, with up to 4-6 centers contributing 50 patients (maximum of 20 patients per center). A sample size of 25 randomly assigned patients per study group (50 subjects in total) was calculated to detect a clinically significant treatment effect of MONTAGE (90% power; alpha = 0.05, 2-sided; 10% lost-to-follow up). This calculation was performed with the assumption that subjects within the control group lose on average 1,500 mL (+/- 500mL) of blood postoperatively while subjects within the treatment group will lose 1,000 mL of blood postoperatively.

3.2 SUBJECT SOURCES

Adult subjects referred to hospital or community-based clinics for treatment of spinal deformity will be eligible for the study.

3.3 SELECTION CRITERIA

The following criteria must be met before a subject is recruited to the trial:

3.3.1 Inclusion Criteria

1. Subject is at least 18 years old, and not more than 80 years old.
2. Presence of spinal deformity requiring a PSO at a single site level, such as for patients with thoracolumbar kyphotic deformity, sagittal imbalance, and spinal global malalignment.
3. Non-smokers (have proven to quit smoking for at least 6 months prior to surgery) and current smokers

3. Female subjects of childbearing potential must be willing to use acceptable methods of contraception (birth control pills, barriers, or abstinence). A pregnancy test at the Week 0 visit must be administered, and must be negative, for inclusion into the study.
4. Subject understands and is willing to participate in the clinical study and can comply with required visits and the follow-up regimen.
5. Subject has read and signed the Institutional Review Board (IRB)/Independent Ethics Committee (IEC) approved Informed Consent Form before screening procedures are undertaken.

3.3.2 Exclusion Criteria

1. Subjects whose spinal deformity is deemed by the investigator to be of such severity that a possible surgical intervention would be either harmful or not warranted.
2. Subjects with morbid obesity (i.e. a Body Mass Index [BMI] \geq 40).
3. Subjects who have a known allergy to the components of MONTAGE.
4. Subjects who are non-mobile (i.e. not ambulatory, or have significant impairment of their mobility making them completely bedridden).
5. Subjects who, in the opinion of the investigator, show evidence of infection, cellulitis, and/or osteomyelitis.
6. Subjects with abnormally low platelets, abnormal coagulation parameters, or with documented bleeding disorders, including a prior history of excessive bleeding during surgery.
6. Subjects with a history of a malignancy, not in remission for five years or more, or a newly diagnosed malignancy, treated with cytotoxic therapies or radiation therapy.
7. Subjects on any investigational drug(s) within 30 days preceding randomization (i.e. Week 0); or subject or physician anticipates use of any of these therapies by the subject during the course of the study.
8. Subjects with:
 - (ii) Alcohol abuse as recorded by an average daily intake of > 4 units in females, > 5 units in males (i.e. 1 oz. of spirit, glass of wine, or can of beer per unit).
 - (iii) Drug abuse as evidenced by the subject's use of illegal drugs or prescription drugs that have not been prescribed for him/her.
9. Subjects with one or more medical conditions, as determined by medical history, including renal, hepatic, hematologic, active auto-immune or immune diseases that, in the opinion of the Investigator, would make the subject an inappropriate candidate for this study.
10. Subjects with a history of osteoporosis, as defined by imaging, or on medication for osteoporosis or documented fracture of fragility (Hip fracture, osteoporotic compression fracture, distal radius fracture). If there are any concerns these may be arbitrated by the study PI.
11. Subject has previously participated in any MONTAGE trial.
12. Subjects who are unable to understand the aims and objectives of the trial and/or unwilling to return for the follow-up examinations..

3.4 WITHDRAWAL

Subjects may drop out or be withdrawn at their own request. Although subjects need not give a reason for requesting withdrawal from the trial, the investigator should make a reasonable effort to ascertain the reason(s), while fully respecting the subject's rights.

4. TRIAL DESIGN AND METHODOLOGY

4.1 TRIAL DESIGN

This study will be an open, prospective, multicenter, randomized, and controlled study to evaluate the effects of MONTAGE® on blood loss and maintenance of the PSO corrective surgical procedure. Patients will be randomized to receive either standard of care (no bone hemostat) or MONTAGE. Within each study group, patients will be stratified according to their smoking status (non-smokers versus current smokers).

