6.3.1 Subject Analysis Sets18

6.3.2	Secondary Variables and Analyses	19
6.3.3	Safety	19
6.3.4	Other Data Summaries	19
7.	ADDITIONAL INFORMATION	19
7.1	USE OF ADDITIONAL MEDICAL SERVICES.....	19
7.2	SOURCE DATA VERIFICATION (SDV).....	19
7.3	TRIAL MONITORING.....	19
7.4	USE OF TRIAL FINDINGS.....	20
8.	ETHICAL AND LEGAL ISSUES	20
8.1	GOOD CLINICAL PRACTICES (GCP).....	20
8.2	APPROVAL OF PROTOCOL.....	20
8.3	CONFIDENTIALITY.....	20
8.4	INSURANCE/FINANCIAL.....	20
8.5	SUBJECT CONSENT.....	20
9.	REFERENCES	22

List of Abbreviations

AE	Adverse Event
cm	Centimeter
CRA	Clinical Research Associate
CRF	Case Report Form
FDA	U.S. Food & Drug Administration
GCP	Good Clinical Practice
ICH	International Conference on Harmonization
IEC	Independent Ethics Committee
in	Inch
IRB	Institutional Review Board
ITT	Intention-to-Treat
ODiv2.1a	Oswestry Disability Index version 2.1a
QoL	Quality-of-Life
SAE	Serious Adverse Event
SRS-22	Scoliosis Research Society -22 Outcomes
UADE	Unexpected Adverse Device Effect
VAS	Visual Analog Scale back and leg pain

SUMMARY

Title:	A Prospective, Multicenter, Randomized, Controlled Clinical Investigation of MONTAGE in Adults with Spinal Deformity undergoing Pedicle Subtraction Osteotomy
Short Title:	MONTAGE in PSO for Adult Spinal deformity
Protocol Number:	Montage 001-2017
Phase:	Phase 4-postmarketing
Methodology:	Prospective, randomized, open, controlled study
Study Duration:	2 years from entry of last subject
Follow-up:	2 years
Study Centers:	Multicenter study with up to 4-6 centers
Objectives:	Primary: To assess the safety and effectiveness of MONTAGE in reducing post-operative blood loss Secondary: To assess the PSO stability
Number of Subjects:	50 subjects
Diagnosis and Main Inclusion Criteria:	
 1. Presence of spinal deformity requiring a PSO 2. Patients aged 18-80 and 3. Non-smokers (must have quit smoking 6 months prior to surgery) and current smokers
Study Product, Dose, Regimen:	After surgically creating the wedged PSO defect, prior to closure of the osteotomy, patients will be randomized 1:1 to receive either MONTAGE applied to the cut surfaces for the osteotomy site or no hemostatic material.
Duration of Administration:	1 application during surgery
Reference Therapy:	Standard of care – no bone hemostat.

End-points and Statistical Methodology:

Efficacy Endpoint:

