4.1.2 SAFETY OBJECTIVES

Safety objectives will include:

- Evaluation of the repaired osteotomy by measuring displacement of the edges of the bone under compression. The angular measurement is the angle between the superior endplate of the vertebral body below the PSO and the inferior endplate of the vertebral body above the PSO. Consistent with the standard of care, successful reconstruction of the osteotomy site requires observation of the residual

angle of the osteotomy and any gap that may be present. In order to demonstrate that the use of Montage does not negatively impact the desired outcome, any residual gap will be measured in millimeters and compared between the groups. This will be done by including a CT scan performed at 1-year post surgery. A 2-sided “t” test will be used for the analysis.

- To demonstrate that Montage does not interfere with the repair, evaluation of the formation of new bone, as measured by CT scans at 1-year post surgery.
- Evaluation using the VAS back pain and leg pain, Oswestry Disability Index (ODIv2.1a) and SRS-22, which will be recorded during the study and reported as outcomes scores, and compared between the two groups.
- Antifibrinolytics use and type will be recorded during the study and compared between the two groups

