4.2 TREATMENT METHODOLOGY

MONTAGE will be used only at a focal site where the osteotomy is performed. It will be applied to the edges of the spine defect after removal of the wedge. MONTAGE will be applied immediately prior to placing the osteotomy site under compression prior to its hardening so as to ensure no interference with compression against the osteotomy edges. Participating investigators, at their discretion, may use autograft and allograft bone void fillers for the other parts of the spine fusion as part of standard of care.

A teaching video will be used to ensure strict adherence to the study procedure at all sites.

Hematological parameters, such as Hb, Hematocrit, RBC, WBC, platelet counts, MCV, MCHC, and differential counts will be recorded and compared between the groups at baseline, immediate post-surgery, and daily up until day 7 or discharge (whichever comes first).

All standard-of-care blood values, including CBC, electrolytes, liver function and kidney function tests during the initial hospital admission will be recorded and analyzed at certified laboratories.

Consistent radiographic parameters will be used to evaluate the angular measurements between the superior endplate of the vertebral body below the PSO and the one above it.

All radiographic images will be read by two reviewers, without knowledge of treatment groups (i.e., blinded).

The radiographic techniques that will be employed in this study are X-rays and CT scans of the thoracolumbar spine without contrast, focusing on the vertebral segments above the osteotomy, the osteotomy segment itself, and the spinal area just below the osteotomy procedure. All images during the study will be read by the same two reviewers.

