4.2.3 Treatment

4.2.3.1 Visit #2: Treatment Phase (Week 0)

The patient will undergo the surgical intervention, excising a bone wedge from the vertebral body followed by a closure of the defect and re-apposition of the bony edges, creating the correction. Just prior to closure of the osteotomy, either MONTAGE or no bone hemostat will be placed on the surface of the cut bone.

Operative parameters, including surgery time (duration of surgery) level of the osteotomy and type of surgery, as well as intra-operative blood loss will be recorded.

The use of anti-fibrinolytics will be recorded.

Regular blood values, including Hb, Hematocrit, RBC, WBC, platelet count, MCV, MCHC and differential counts will be performed on each post operative day while subject is in the hospital, up until day 7.

Number of blood transfusions as well as any wound drain output will also be recorded.

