5.1 ADVERSE EVENT

An adverse event (AE) is defined as any unfavorable or unintended sign, symptom, or disease temporally associated with the use of the study products, or worsening of a pre-existing condition, whether or not it is considered related to the study treatment. All AEs and intercurrent illnesses must be recorded in the subject's medical records and on the CRF.

Adverse events will be defined as those events that occur after signing the informed consent until the final study visit. A description of the AE along with the onset date, end date, severity, action taken, treatment, outcome, likely cause, and relationship to the study products will be recorded in the CRF.

Local and systemic AEs associated with each treatment arm will be tabulated and compared. AEs will be elicited through direct questioning, subject reports, and physical examination.

An abnormal laboratory test result is not by itself considered to be an AE unless the Investigator considers the finding of clinical significance that should be reported in such a manner.

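### The trial is open except for its image readers; keeping the patient unaware of the arm looks feasible and would reduce, though not remove, bias in pain, ODI, SRS-22 and self-reported adverse events.

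*Combined protocol and SAP*

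**What the plan says.** The Summary, Section 4.1 and Section 6.1 all describe an open trial. Section 4.1 reads: "This study will be an open, prospective, multicenter, randomized, and controlled study". Section 6.1 reads: "This is a parallel group, randomized, open, multicenter, prospective study". No section gives a reason for leaving the patient unblinded.

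There is one exception. Section 4.2 states: "All radiographic images will be read by two reviewers, without knowledge of treatment groups (i.e., blinded".

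The Summary describes the comparator as "Standard of care – no bone hemostat". Section 4.2.3.1 fixes the moment of treatment: "Just prior to closure of the osteotomy, either MONTAGE or no bone hemostat will be placed on the surface of the cut bone". Sections 4.2.3.2 to 4.2.3.7 and Appendix I give one schedule of visits, imaging and questionnaires for both arms.

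Section 4.1.2 lists among the safety objectives: "Evaluation using the VAS back pain and leg pain, Oswestry Disability Index (ODIv2.1a) and SRS-22, which will be recorded during the study", with a comparison between groups. Sections 1.4 and 6.1 list the same scores as secondary. On adverse events, Section 5.1 states: "AEs will be elicited through direct questioning, subject reports, and physical examination", and adds that events will be tabulated and compared by arm. Section 5.1.1 makes the investigator responsible for causality and mentions no blinding.

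**The concern.** Pain, disability and SRS-22 scores come from the patient, and so do many adverse event reports. A patient who knows the arm may answer differently because of it. If that knowledge improves scores in the MONTAGE arm, a real worsening of similar size could go unseen. If it makes patients with a new implant more watchful, the product could look worse than it is. Analysis cannot separate either effect from a treatment effect afterwards.

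Many surgical trials cannot avoid this, because the patient can see or feel what was done. Here the product goes onto cut bone inside the osteotomy, the control is simply its absence, and the plan describes no after-care that differs by arm. The exposure therefore looks avoidable for the patient, and the plan does not say why it is accepted.

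**Working it through.** **Who is blinded, by outcome**

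| Outcome | Source | Blinded in the plan? |
|---|---|---|
| Gap, angle, fusion, new bone | Two image readers (4.2) | Yes |
| Blood loss by formula | Hematocrit, transfused red cells and cell saver (4.1.1) | Not stated; largely a laboratory measure |
| VAS, ODI, SRS-22 | Patient (4.1.2; 4.2.3.2 to 4.2.3.7) | No |
| Adverse event reports | Patient report, questioning and examination (5.1) | No |
| Adverse event causality | Investigator, with a further assessment by the sponsor's medical assessor (5.1.1) | Not stated |

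**Does anything require the patient to know?** Treatment is a single application during surgery (Summary, 4.2, 4.2.3.1). The documents do not mention anaesthesia, but it is a safe inference for an open spinal osteotomy. The later schedule is common to both arms. On the documents, nothing after surgery depends on the patient knowing.

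**When is the arm known?** Three places differ:
- The Summary places randomization during surgery, after the wedge defect is made: "prior to closure of the osteotomy, patients will be randomized 1:1 to receive either MONTAGE".
- Section 4.2.2 places it after the center has submitted preoperative data.
- Appendix I marks it at Baseline/Screening.

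Under the last two, the site may know the arm before surgery, and the patient could learn it then.

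**The plan's own sample size.** Section 3.1 gives means of 1,500 and 1,000 mL, SD 500 mL (reading the plus/minus figure as the SD), 90% power, two-sided alpha 0.05 and 10% loss.
- n per arm = 2 × (1.960 + 1.282)² × (500/500)² = 21.0, which the normal-approximation calculation rounds up to 22.
- Allowing for loss: 22 / 0.90 = 24.4, rounded up to 25 per arm, or 50 in total.

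This reproduces the stated figure. Blinding the patient changes none of these inputs.

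**Illustration of a reporting shift.** The size of the shift is an assumption. With 10% loss, 50 × 0.90 = 45 patients remain, taken as 22 and 23. Assume no true difference, a shift of b SD caused only by knowing the arm, and a two-sided t-test at 0.05.
- Degrees of freedom: 22 + 23 − 2 = 43; critical value 2.017.
- Noncentrality: b × √(22 × 23 / 45) = 3.353 × b.

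| Assumed shift (SD) | Noncentrality | Chance of p < 0.05 |
|---|---|---|
| 0 | 0 | 5.0% |
| 0.2 | 0.67 | 10.1% |
| 0.3 | 1.01 | 16.6% |
| 0.4 | 1.34 | 25.9% |

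These figures are for one score at one visit. The same calculation bears on masking. With no reporting shift, a true harm of 0.3 SD would reach significance 16.6% of the time; with an opposing shift of 0.3 SD that falls to 5%.

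**The case against.** The strongest reply is that this is a consistent design choice for a post-marketing study of a cleared device, and that the outcomes that matter most are protected. Much of that stands.

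- A reader might infer that the trial is fully open. It is not: image reading is blinded, which covers gap, angle, fusion and new bone.
- A reader might infer that the patient-reported scores carry the no-harm claim. In Section 4.1.2 the explicit wording to that effect is attached to the residual gap and to new bone formation, both read from CT by blinded readers. The Summary plans descriptive statistics for the scores, and Section 6.3.2 calls secondary analyses exploratory. The scores are still listed as safety objectives and compared between arms, and describing a biased mean does not make it unbiased.
- A reader might infer that the bias must favour MONTAGE. The documents do not support a direction. Section 8.5 requires consent to cover both positive and negative effects of the material, and no section says that patients are told their arm; the plan simply does not keep it from them.
- A reader might infer that the primary result is compromised through unblinded transfusion decisions. The formula in Section 4.1.1 adds transfused red cells to the fall in hematocrit, and a transfusion also raises hematocrit, so discretionary transfusion is largely offset. Transfusion need and drain output, which Section 1.4 includes in the primary objective, remain open to influence by staff who know the arm. The documents give no basis for sizing that.
- Power to see a modest harm on these scores is low even without bias, so blinding recovers only part of what is missing.
- Blinding the patient would not remove the bias. The surgeon knows the arm, the investigator who attributes adverse events may know it, and a patient may learn it from the medical record or from images on which the material might be visible.

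**Conclusion.** The point holds as an inexpensive improvement to the design. It is not an error or a contradiction in the plan. The trial is open except for its image readers, the patient does not need to know the arm, and self-reported outcomes through Week 104 are left exposed without a stated reason. The size and direction of any bias are unknown. The range of 10% to 26% rests on an assumed shift of 0.2 to 0.4 SD, 45 evaluable patients, and a significance test that the Summary does not plan for these scores; it shows sensitivity and does not estimate the bias. The conflict over the timing of randomization is in the documents themselves and needs resolving in any case, since concealment from the patient depends on it.

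**What to change.** 1. In the Summary, Section 4.1 and Section 6.1, replace the term open with patient- and image-reader-blinded.
2. State in the consent form that the arm will be disclosed after the Week 104 questionnaires, or earlier on medical need.
3. Have patients complete VAS, ODI and SRS-22 themselves.
4. Record the arm on a separate operative CRF page, and do not routinely tell ward staff. Log every unblinding with its date and reason.
5. Reconcile the Summary, Section 4.2.2 and Appendix I on when randomization takes place, so that the arm is not revealed to the patient before surgery.

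If the sponsor prefers to keep patients unblinded, Section 4.1 should say why.

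The cost is consent wording, CRF layout and handling of the operative record. On the documents this needs no extra patients, visits or procedures, though the effort at sites cannot be checked from them. The remaining weaknesses are an unblinded surgeon, adverse event causality assigned by an investigator who may know the arm, and some patients learning their arm. The report should acknowledge these.
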